3.2.4.3 Pharmacodynamic Effects

Tumor and skin biopsies obtained before the first and planned fifth infusions of Sym004 in trial Sym004-01. A decrease in membranous EGFR expression and decreases in the proliferation marker, Ki67, were observed in both tumor and skin biopsies (13). These data provided clinical proof that Sym004 at the doses administered distributed to tumor, inhibited the intended target, and suppressed a known marker of tumor growth.

3.2.4.4 Antitumor Effects

As a part of the Phase 1 Sym004 dose-escalation trial (Sym004-01), antitumor activity was documented in patients with mCRC resistant to anti-EGFR antibody therapy (13). Five of the 39 documented refractory patients (13%) with adequate imaging studies achieved a partial response (PR). These responses were confirmed by independent radiologic review. A PR or disease stabilization, Stable Disease (SD), was documented in 67% of patients with available assessments. An exploratory analysis revealed that the responders to Sym004 were shown to have tumors with WT KRAS, NRAS, and BRAF genotype, as well as having no

evidence of MET amplification. One of the responder's tumors expressed an EGFR mutation (EGFRS492R) at baseline, a marker that is associated with resistance to cetuximab.

3.3 Trial Rationale

Although the use of anti-EGFR mAbs is well established in the treatment of mCRC, only a minority of patients with advanced disease respond to the approved antibodies alone or in combination with chemotherapy (3-8). Patients who do respond initially, ultimately become resistant to combined therapies, including the currently approved anti-EGFR mAbs. The overall magnitude of clinical effects observed with anti-EGFR antibodies alone or in combination has been limited, and patients who develop resistance have few treatment options (3-8). The distinct mechanism of action of Sym004 (9), compared to available anti-EGFR mAbs, as well as the promising nonclinical and clinical data documenting activity in models (9-11) and patients with mCRC refractory to prior anti-EGFR antibody therapy (13), provide strong support for the trial of Sym004 in combination with FOLFIRI therapy in patients with CRC, who have progressed following first-line therapy, but have not received prior therapy with an EGFR inhibitor.

Following treatment with EGFR inhibitors, such as cetuximab and panitumumab, tumors may develop resistance to the treatment. Varieties of trials have documented alterations in tumor cells that may be involved in acquired resistance to anti-EGFR therapies (14). One reported mechanism of resistance is based on increased production of EGFR ligands (15). Sym004 may be able to overcome this resistance mechanism by eliciting a more pronounced down-regulation of the expression of EGFR (9-11,13) than observed with the approved monoclonal anti-EGFR antibodies. This hypothesis is supported by the demonstration of clinical activity in patients considered to be resistant to anti-EGFR mAbs, with an observed response rate after treatment with Sym004 in a range otherwise expected for cetuximab and panitumumab in patients who have not received an anti-EGFR mAb (13).

Based on the above-cited data, this Phase 1b/2a trial is designed to first evaluate the safety and tolerability of Sym004 in combination with FOLFIRI in order to determine the Maximum Tolerated Dose (MTD) and the Recommended Phase 2 Dose (RP2D). Upon delineation of the RP2D, additional patients who have failed first-line therapy for CRC will receive the combination to assess the antitumor activity of this regimen. The preliminary data suggesting both a different mechanism of action as well as activity of Sym004 in patients with CRC refractory to cetuximab, provides a rationale for improved activity in earlier lines of therapy in patients without acquired resistance to anti-EGFR antibodies.

As of Amendment 3: This amendment to the clinical trial protocol (CTP) is based on a Sponsor decision to discontinue the development of Sym004 in combination with FOLFIRI. As a result, enrollment has stopped and a reduction in the total scope of non-safety related assessments being conducted under this CTP will be implemented.

Patients who are actively being treated with Sym004 alone or in combination with FOLFIRI may continue therapy until unacceptable toxicity or other conditions preventing further administration, progressive disease (PD), or patient's decision to withdraw. Patients no

longer receiving Sym004 alone or in combination with FOLFIRI should be discontinued from study participation. Refer to [Section 7.6](#).

Patients will continue to be followed and assessed for clinical safety-related concerns throughout their respective treatment periods and at minimum for 30 days after the last administration of Sym004.

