5.3 Schedule of Events

The overall trial plan is introduced in [Table 1](#) and further defined in the below sections.

Table 1 Overall Trial Plan

Screening Period	
Screening	14 days within first dose of Sym004 + FOLFIRI
Treatment Period	
Treatment Allocation	The allocated dose of Sym004 will depend upon cohort assignment of Sym004 and will be confirmed by the Sponsor or designee on an allocation form FOLFIRI is given as a standard dosing regimen to all patients
Sym004 + FOLFIRI	The trial treatments will consist of Sym004 in combination with FOLFIRI. Sym004 and FOLFIRI are both initiated on C1/D1 and will be administered every second week by iv infusion (Day 1 and Day 15 of each 28 day cycle [± 2 days]). The Sym004 infusion will be delivered first. The FOLFIRI regimen administration will commence no sooner than 1 hour following completion of Sym004 administration.
Discontinuation of Sym004 and/or FOLFIRI*	Treatment will continue in cycles of 28 days (± 2 days) until unacceptable toxicity or other conditions preventing further treatment, PD, termination of the trial or patient's decision to withdraw. Sym004 and FOLFIRI may be discontinued simultaneously or one may be discontinued before the other. The schedule for the treatment period will apply from the initiation of Sym004 and FOLFIRI until both Sym004 and FOLFIRI have been discontinued.
End of Treatment	
End of Treatment (EOT)*	Within 10 days after the decision to discontinue Sym004 and FOLFIRI (or the last of the two), an EOT Visit must be performed
Follow-up	
One Month Follow-up (1M FUP)*	Follow-up continues until 1 month (28 + 7 days) after the last dose of Sym004/FOLFIRI. At that time, a 1M FUP Visit must be performed. This 1M FUP visit constitutes the end of trial participation for the patient.

Abbreviations (in alphabetical order): C1/D1, Day 1 of Cycle 1; EOT, End of trial treatment Visit (Sym004 and FOLFIRI); 1M FUP, One Month Follow-up Visit

***As of Amendment 3:** The schedule for the treatment period will apply from the initiation of Sym004 and FOLFIRI until Sym004 has been discontinued. An EOT Visit will be performed within 10 days from the decision to withdraw treatment with Sym004, and a follow-up visit will be performed 1 month after the last administration of Sym004.

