5.3.4 End of Treatment and One Month Follow-up Visit

An EOT Visit will be performed for all patients within 10 days after the decision to discontinue treatment with all trial medications (i.e. only once both Sym004 and FOLFIRI have been discontinued).

The patient will return for follow-up 1 month (28+7 days) after the last dose of Sym004/FOLFIRI, whichever is last (i.e. only once both Sym004 and FOLFIRI have been discontinued). This will be the 1M FUP Visit.

As of Amendment 3: An EOT Visit will be performed for all patients within 10 days after the decision to discontinue treatment with Sym004. The patient will return for follow-up 1 month after the last administration of Sym004.

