5.3.5 Flow Chart – Schedule of Assessments

A complete schedule of assessments is provided in the trial flow chart in [Table 2](#).

All efforts should be made to perform assessments as close as possible to the scheduled time points. Visit windows are included in the flow chart.

Table 2 Flow Chart – Schedule of Assessments

Pre-Treatment Phase		Treatment Phase ¹								Post-Treatment Phase	
Cycle Number	Screening	Cycle 1				Cycle 2, 4, 6 etc.		Cycle 3, 5, 7 etc.		EOT	1M FUP
Day within Cycle Visit Window (± days)	D-14 to D-1	D1	D8 (±2)	D15 (±2)	D22 (±2)	D1	D15 (±2)	D1	D15 (±2)	≤ 10 d from the decision of trial treatment withdrawal	1 month after last dose of trial treatment (28+7d)
Informed Consent	X										
Baseline Characteristics/Eligibility ²	X	X									
Safety Assessments											
Medication Survey	X	X	X	X	X	X	X	X	X	X	X
(S)AE Survey and Reporting	X	X	X	X	X	X	X	X	X	X	X
DLT Evaluation (dose-escalation only) ³		X	X	X	X	C2/D1					
Vital Signs and Body Weight	X	X		X		X	X	X	X	X	X
ECOG PS	X	X				X		X		X	X
Physical Examination	X	X				X		X		X	X
Dermatological Examination	X	X		X		X	X	X	X	X	X
ECG ⁴	X									X	
Safety blood samples ⁵	X	X	X	X	X	X	X	X	X	X	X
Urinalysis ⁵	X	X		X		X		X		X	X
Pregnancy Test	X									X	
Disease Assessments											
(Archival) Tumor Biopsy Collection ^{6,7}	X										
Tumor Marker Evaluation ⁸	X						End of C			X	X
Disease Status Evaluation by CT/ MRI ^{9,10}	X						End of C			X	X
*Additional Assessments											
*PK Samples (dose-escalation only) ¹¹		X		X		X	X	X		X	X
*ADA Sample		X						X		X	X
*Biomarker Blood and Urine Sample ¹²	X						End of C2			X	
Trial Treatment											
Skin Toxicity Prophylaxis and TX ¹³		X	X	X	X	X	X	X	X	X	X
Infusion Reaction Prophylaxis ¹⁴		X		X							
Sym004 Infusion		X		X		X	X	X	X		
Gastrointestinal Toxicity Prophylaxis ¹⁵		X		X		X	X	X	X		
FOLFIRI Infusion		X		X		X	X	X	X		
Post-Infusion Monitoring		X		X		X	X	X	X		

Abbreviations (in alphabetical order): ADA, anti-drug antibody; C, Cycle; CT, computed tomography scan; D/d, day(s); DLT, dose-limiting toxicity; EOT, End of trial treatment Visit (Sym004 and FOLFIRI); ECG, electrocardiography; ECOG PS, Eastern Cooperative Oncology Group performance status; MRI, magnetic resonance imaging; 1M FUP, One Month Follow-up Visit; PK, pharmacokinetic; (S)AE, (serious) adverse event; TX, therapy

*Omitted with Amendment 3

- 1) The treatment phase continues until the patient is withdrawn from Sym004 (**As of Amendment 3**)

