9.2 Adverse Event Recording and Reporting Instructions

9.2.1 Adverse Event Recording Period

All AEs will be recorded from signing the informed consent. The recording period ends at the time of the 1M FUP Visit.

NOTE: Patients who sign the informed consent and are subsequently deemed to be screening failures will be followed for the occurrence of SAEs/AEs until it is determined they will not be participating in the trial.

The Investigator must record all directly observed AEs and all AEs spontaneously reported by the patient. A general, open-ended type of question should be used to elicit a response from the patient, such as, “Do you have any health problems?” or “Have you had any health problems since your last visit?”.

All AEs that occur in patients during the AE recording period must be recorded/entered on the AE section of the Case Report Form (CRF), whether or not the event is assessed as related to Sym004. If the AE is serious, the SAE report forms must also be completed and submitted (see [Section 9.3](#)).

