9.2.6 Follow-up of Adverse Events

All AEs should be followed until they are resolved or until the 1M FUP Visit, whichever comes first.

NOTE: Patients who sign Informed Consent and are subsequently deemed to be screening failures will be followed for the occurrence of SAEs/AEs until it is determined they will not be participating in the trial.

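### Amendment 3 promises at least 30 days of safety follow-up after the last Sym004 dose, but the visit that ends adverse event recording may be held from Day 28

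*Protocol*

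**What the plan says.** Two sets of current statements bear on how long safety is followed after the last Sym004 dose.

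- **The minimum.** The Synopsis (Design and Plan) and Section 3.3, both in text marked as of Amendment 3, say patients are followed for safety through treatment and "at minimum for 30 days after the last administration of Sym004".
- **The visit.** Table 1 in Section 5.3 says "Follow-up continues until 1 month (28 + 7 days) after the last dose of Sym004/FOLFIRI". Section 5.3.4 says "The patient will return for follow-up 1 month (28+7 days) after the last dose of Sym004/FOLFIRI, whichever is last". The 1M FUP column of Table 2 reads "1 month after last dose of trial treatment (28+7d". Section 6.3 gives the same 28+7 days.
- **The Amendment 3 change to the visit.** Section 5.3.4 adds "The patient will return for follow-up 1 month after the last administration of Sym004". Similar sentences stand in Sections 5.1 and 6.3 and under Table 1. They change the starting point to Sym004 alone and give no number of days.
- **What the visit ends.** Section 9.2.1: "The recording period ends at the time of the 1M FUP Visit". Section 9.2.6: "All AEs should be followed until they are resolved or until the 1M FUP Visit, whichever comes first". Table 1: "This 1M FUP visit constitutes the end of trial participation for the patient".

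Section 9.3 adds that SAEs still ongoing at the visit are followed until resolved, chronic or stable. A new SAE after the visit is reported only if the investigator learns of it and finds it related to the product or to trial conduct, and it then goes only to the safety database.

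**The concern.** A site that sees the patient 28 days after the last Sym004 dose has kept to the visit schedule, and AE recording closes that day. The same site has not met the 30-day minimum, and nothing else in the Protocol carries AE collection on to Day 30.

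What is at stake is a stated commitment. Amendment 3 reduces the trial to mainly safety-related evaluation, and the 30-day minimum is the follow-up it undertakes to provide. As written, the sponsor could not say that every patient who followed the schedule received it.

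**Working it through.** This is a day count, with days numbered from the last Sym004 dose.

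**Inputs**
- Stated minimum: 30 days (Synopsis; Section 3.3).
- Visit: 28 days with a window of +7 (Table 1; Table 2; Sections 5.3.4 and 6.3).
- AE recording ends on the day of the visit (Section 9.2.1). Follow-up of unresolved AEs ends then too (Section 9.2.6).

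**Permitted visit days**
- Earliest = 28 + 0 = Day 28.
- Latest = 28 + 7 = Day 35.
- Number of permitted days = 35 − 28 + 1 = 8.

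**Comparison with the minimum** (shortfall = 30 − visit day, where positive)

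| Visit day | Within schedule | Shortfall against 30 days |
|---|---|---|
| 28 | yes | 30 − 28 = 2 days |
| 29 | yes | 30 − 29 = 1 day |
| 30 to 35 | yes | none |

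Two of the eight permitted days miss the minimum, and six (35 − 30 + 1) satisfy both statements.

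**Could another reading of the visit remove the conflict?**
- *28+7 as a fixed Day 35.* This would meet the minimum, but it does not fit the label of one month or the visit-window row at the head of Table 2. Section 7.5.2, which uses the same figure with the words for not less than, also points to 28 as a lower edge.
- *One calendar month, as the Amendment 3 sentences might be taken.* A calendar month runs from 28 to 31 days, so it does not guarantee 30 either.
- *28 days with a +7 window.* This is the natural reading and the only numerical definition left in the text. It gives the shortfall above.

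**What falls in the gap.** After a Day 28 or 29 visit and up to Day 30, Section 9.3 still covers SAEs already ongoing and new SAEs that the investigator becomes aware of and judges related. Non-serious AEs that start in the gap, and new SAEs not judged related, are not captured.

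**The case against.** The strongest reply is that the two statements are compatible. One is a minimum and the other a permitted range, so a site reading the whole Protocol can choose any of Days 30 to 35. The Amendment 3 sentences also say only one month, so the Day 28 start rests on retained text and the Table 2 header. Both points are fair, and it would be wrong to call the rules mutually exclusive. But the schedule is what sites work from, Table 2 carries Amendment 3 footnotes and still shows 28+7 days, and nothing tells a site to avoid Days 28 and 29.

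Several stronger readings that a reader might infer are not supported:

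- *That the safety analysis is compromised.* No analysis in Section 10 uses a Day 30 cut-off. Section 10.4.1.1 counts events after first treatment, with reporting to the end of trial participation, and Section 10.4.1 makes the safety presentation descriptive only.
- *That two of eight days means a quarter of patients.* It is a count of calendar days. The Protocol gives no distribution of visit dates and names no target day; Day 28 is the lower edge of a one-sided window.
- *That uneven capture between patients comes from this mismatch.* Any flexible window lets collection end on different days. It would still do so with visits allowed on Days 30 to 35.
- *That safety is the only thing still collected.* Section 10.6 keeps efficacy follow-up the sponsor considers necessary, and the imaging and tumor marker rows of Table 2 are not marked as omitted.
- *That all SAEs are lost after the visit.* Section 9.3 retains the ongoing and the related ones.

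**Conclusion.** The inconsistency is real and lies in current body text, not in the amendment log. A visit that complies with the schedule on Day 28 or 29 ends AE collection 1 to 2 days short of the minimum set in the Synopsis and Section 3.3.

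Its size is small. The shortfall is at most 2 days, the uncovered events are non-serious AEs and new SAEs not judged related, and no planned estimate or table depends on it. Enrollment has stopped (Section 5.5), so it concerns only patients still on Sym004.

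The conclusion rests on two assumptions: that 28+7 days is Day 28 with a seven-day allowance, and that this definition still applies once Amendment 3 moves the starting point to the last Sym004 dose. The documents do not show whether 30 days or 28 days was intended, so they do not support calling either figure the error. It is worth correcting because it costs almost nothing and makes a stated safety commitment deliverable.

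**What to change.** Reconcile the 30-day minimum with the 28+7-day window in Table 1, Table 2, and Sections 5.3.4 and 6.3, counting from the last Sym004 dose as Amendment 3 does. Any of these would do it:

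- Set a 1M FUP window whose lower edge is not below the stated minimum, leaving the outer limit at Day 35. With 30 days kept, the window shrinks from 8 permitted days to 6 (Days 30 to 35), with no added visit.
- Keep the visit window, and let AE recording and follow-up in Sections 9.2.1 and 9.2.6 run to the stated minimum when the visit falls earlier. This needs a way to collect events after the visit, and the statement in Table 1 that the visit ends participation would have to agree.
- Restate the minimum in the Synopsis and Section 3.3 to match the existing window. The cost is a slightly shorter stated follow-up.

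The sponsor should choose and say which figure was meant.

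Check Sections 5.6 and 7.5.2 separately, and do not paste the same wording into them. Both use 28+7 days but count from withdrawal from trial treatments, and Section 5.6 is an outer limit on the end of the trial. Inserting a window counted from the last Sym004 dose there would change those rules without notice.

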3.4 Dose Rationale

The starting dose of Sym004 in the trial is based upon prior demonstration that a dose of 12 mg/kg administered weekly was determined to be the RP2D on this schedule although no MTD was formally reached. The safety and tolerability of this dose level on both a weekly and every second week schedules are outlined above and greater detail is available in the IB. In addition, preliminary antitumor activity in patients with mCRC and acquired resistance to available anti-EGFR mAbs was observed after administration of weekly doses of Sym004 of 9 mg/kg or 12 mg/kg (13). Doses of 12 mg/kg and 18 mg/kg have furthermore been tolerated on an every second week schedule (16).

3.5 Overall Benefit/Risk

As previously discussed, Sym004 has been documented to be active in preclinical studies using cetuximab-resistant tumors, as well as in preliminary clinical trials in mCRC and SCCHN patients with acquired resistance to anti-EGFR mAbs (13,17). The activity of Sym004, in patients refractory to therapy with mAbs targeting the EGFR, was similar to the single agent activity seen with these agents in treatment-naïve mCRC patients.

In previous trials, Sym004 showed an acceptable safety profile. The safety profile was similar to that of other anti-EGFR antibodies, although for both skin toxicities and hypomagnesemia the percentage of patients with grade 3 skin toxicities and grade 3/4 hypomagnesemia appeared to be higher (13,17).

The continued unmet need for alternative treatments for mCRC, the available data on the safety, and preliminary data on antitumor activity of Sym004 (13), have been considered in evaluating the risk-benefit relationship in the planning of the trial. Based on the preclinical and clinical data available to date, the conduct of the trial is considered justifiable using the doses and dosage regimens of the IMP as specified in this Clinical Trial Protocol (CTP). In this trial, as applicable, there will be an ongoing assessment of the risk-benefit ratio with periodic evaluation of the results including review by external experts in CRC familiar with the use of anti-EGFR antibodies. The trial will be discontinued in the event of any new findings that indicate a relevant deterioration of the risk-benefit relationship that would render continuation of the trial unjustifiable.

In order to mitigate potential risks, the trial is designed to allow for dose de-escalation if the safety and tolerability of the initial dose exceeds the MTD. If the dose is safe and well tolerated, dose-escalation may proceed to establish a RP2D. The potential to slow infusions, interrupt dosing, decrease the doses administered, and to discontinue administration of

Sym004 in the event of specific AEs are outlined. In addition, steps to prevent infusion reactions and measures to intervene in the event of electrolyte imbalances and cutaneous toxicities are specified. Furthermore, prophylactic treatment for FOLFIRI induced diarrhea and vomiting according to institutional standards is required.

The trial will be conducted in accordance with the CTP, the principles of the Declaration of Helsinki (18), ICH E6 GCP (1), and other laws in the countries where the trial takes place.

4 TRIAL OBJECTIVES AND ENDPOINTS

4.1 Dose-Escalation (Phase 1b)

As of Amendment 3: Due to the premature discontinuation of the enrollment of the trial, the primary, secondary, and exploratory objectives are no longer applicable. Clinical safety-related evaluations will continue to be conducted.

4.1.1 Primary Objective

To determine the MTD and/or RP2D of Sym004 when administered by iv infusion every second week in combination with a standard dosing regimen of FOLFIRI (Folinic Acid [FA; leucovorin], 5-fluorouracil [5-FU], irinotecan) to patients with locally advanced or metastatic CRC.

4.1.2 Secondary Objectives

- To determine the safety and tolerability of Sym004 when administered in combination with a standard dosing regimen of FOLFIRI
- Evaluation of the immunogenicity of Sym004
- Characterization of the PK profile of Sym004
- Preliminary evaluation of the antineoplastic effect of Sym004 plus FOLFIRI as assessed by the Response Evaluation Criteria in Solid Tumors (RECIST v1.1) ([Appendix 1](#))

4.2 Dose-Expansion (Phase 2a)

4.2.1 Primary Objective

To evaluate the antineoplastic effect of Sym004 when administered at the RP2D in combination with a standard dosing regimen of FOLFIRI to patients with locally advanced or metastatic CRC.

